#### **4.1.3 Exclusion Criteria**

- Patients with features of age-related macular degeneration such as abundant drusen and demographic features consistent with this diagnosis.
- Allergy to Fluorescein, ICG, Iodine, Shellfish.
- Pregnancy (positive pregnancy test)
- Any other condition that the investigator believes would pose a significant hazard to the subject if the investigational therapy were initiated.
- Participation in another simultaneous medical investigation or trial
- Exclude other anti-VEGF agents as therapy options.
- History of previous subfoveal laser.
- Advanced glaucoma (IOP>25 or cup/disc ratio >0.8)
- Any condition in the opinion of the investigator that would interfere with disease status/progression or jeopardize patients' participation in the study.

#### **4.2 METHOD OF TREATMENT ASSIGNMENT**

This is a non-randomized, open-label study of 2.0 mg Ranibizumab. Treatment assignment will be determined by baseline status of treatment naive vs. previously treated PCV eyes.

#### **4.3 STUDY TREATMENT**

##### **4.3.1 Formulation**

Ranibizumab 2.0mg is formulated as a sterile solution aseptically filled in a sterile 3-mL stoppered glass vial. Each vial contains 0.5 mL of 40 mg/mL (2.0mg dose level) ranibizumab aqueous solution (pH 5.5) with 10 mM histidine HCl, 10% trehalose

dihydrate, and 0.01% polysorbate 20, pH 5.5. The vial contains no preservative and is suitable for single use only. Vials should be protected from direct light.

For further details and molecule characterization, see the Investigator Brochure.

#### **4.3.2 Dosage, Administration, and Storage**

**1. Dosage-** 2.0 mg/0.05 ml Ranibizumab will be given monthly *from Day 0 through Month 2*, and then at the discretion of investigator no more frequent than monthly for months 3-12.

**2. Administration-** Intravitreal Injection *will only be given* at the Southeast Retina Center *location*.

\*See Appendix B for detailed pre-injection procedures.

**3. Storage-** Upon receipt, study drug kits will be refrigerated at 2°C - 8°C (36°F - 46°F). Vials will not be used beyond the expiration date. Ranibizumab vials will remain refrigerated and will not be frozen.

#### **4.4 CONCOMITANT AND EXCLUDED THERAPIES**

Starting at month three (ranibizumab injection #1 at baseline, #2 at month 1, and #3 at month 2), treatment will occur at the discretion of the investigator. Observation is permitted as well as intravitreal 2.0 mg Ranibizumab as frequent as every month for months 3-12. Other anti-VEGF agents, such as Avastin or Macugen® or 0.5mg Ranibizumab, will not be permitted. At the discretion of the investigator, *starting* at month 3 thermal laser, photodynamic therapy with Visudyne®, intravitreal or periocular steroids are permitted, if necessary.

#### **4.5 STUDY ASSESSMENTS**

##### **4.5.1 Assessments during the Treatment Period**

See Section 3.1

#### **4.5.2 Early Termination Assessments**

Subjects who withdraw from the study prior to completion should return for an early termination evaluation 30 days ( $\pm$  7 days) following the last injection/study visit for monitoring of all adverse events (serious and non-serious). The schedule of assessments for early termination is the same as that for the final visit.

### **4.6 SUBJECT DISCONTINUATION**

Subjects have a right to withdraw from the study at any time. The subject may be withdrawn from the study for any reasons: if it is in the best interest of the subject, intercurrent illness, adverse events, or worsening condition. The Southeast Retina Center may request the withdrawal of a subject because of protocol violations, administrative reasons, or any other valid and ethical reasons.

*All non serious and serious* If a subject discontinues from the study, he or she will not be allowed to re-enter the study.

Reasons for subject discontinuation may include, but are not limited to, the following:

- Sensory rhegmatogenous retinal detachment or Stage 3 or 4 macular hole
- Investigator determination that it is not in the best interest of the subject to continue participation
- Pregnancy
- Macugen injection treatment in study eye
- SAE
- Any other safety concerns

In the event of an adverse event in the study eye that is considered by the investigator to be severe in intensity, serious consideration should be given to discontinuing the subject from the study.

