### **2.1 Primary Objective**

To investigate the safety and tolerability of 3 initial intravitreally administered injections of 2.0 mg Ranibizumab with a 9 month PRN treatment period and 12 month off drug safety follow up.

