### **3.3 OUTCOME MEASURES**

#### **3.3.1 Primary Outcome Measure**

The primary outcome measure for safety and tolerability is the following:

Incidence and severity of ocular and systemic adverse events. Examples include 30 letter loss, major subretinal hemorrhage, involving 75% or more of clinical macula (arcade to arcade), disease-related vitreous hemorrhage, injection-related endophthalmitis, retinal detachment, vitreous hemorrhage, *study drug/procedure* -

related uveitis, incidence and severity of other adverse events, as identified by physical examination, subject reporting, and changes in vital signs.

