#### **4.8.4 Missing Data**

Analyses of efficacy and safety will be based on available cases, without imputation for missing values.

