### **5.1 ADVERSE EVENTS**

*All adverse events occurring from Day 0 through Month 12 or Early Withdrawal will be documented and assessed by the principal investigator.* Subjects discontinuing early from the study should return for an early termination evaluation and will be contacted 7 days after their last injection or study visit to elicit for occurrence of adverse events (serious and nonserious).

For this protocol, an AE is any “on study” untoward medical occurrence (e.g., sign, symptom, disease, syndrome, intercurrent illness) that occurs in a study subject, regardless of the suspected cause. “On study” refers to Day 0 through the last study visit.

Unchanged, chronic conditions are NOT AEs and will not be recorded. An exacerbation or worsening of a chronic condition should be recorded as an AE.

Both serious and nonserious AEs should be graded on a three-point scale (mild, moderate, severe) and reported in detail in the subjects clinic record.

The suggested definitions are as follows:

Mild: Discomfort noticed but no disruption of normal daily activity

Moderate: Discomfort sufficient to reduce or affect normal daily activity

Severe: Incapacitating with inability to work or perform normal daily activity

Using the following criteria, the investigator will also assess whether there is a reasonable possibility that study drug caused or contributed to the AE.

- Yes (possibly or probably)

There is a clinically plausible time sequence between onset of the AE and study drug administration; and/or

There is a biologically plausible mechanism for study drug causing or contributing to the AE; and

- No

The AE may or may not be attributed to concurrent/underlying illness, other drugs, or procedures.

A clinically plausible temporal sequence is inconsistent with the onset of the AE and study drug administration; and/or

A causal relationship is considered biologically implausible.

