## **5.5.4 Type And Duration Of Follow-Up After Adverse Events**

All reported AEs should be followed until resolution or until the subject's participation in the study ends. Subjects who have an ongoing study drug-related SAE at study completion or at discontinuation from the study will be followed by the investigator or his or her designee until the event is resolved or determined to be irreversible, chronic, or stable by the investigator.

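### Section 4.6 does not separate stopping study drug from leaving the study, so later safety follow-up can be cut short because of harm

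*Combined protocol and SAP*

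**What the plan says.** The primary objective (2.1) is the safety and tolerability of three initial injections "with a 9 month PRN treatment period and 12 month off drug safety follow up", and section 2 gives 24 months in total. The primary outcome (3.3.1) is "Incidence and severity of ocular and systemic adverse events". In the second year, follow-up consists of telephone interviews about adverse events at Months 18 and 24 (3.1, Appendix A).

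Section 4.6 introduces its list with "Reasons for subject discontinuation may include, but are not limited to, the following". The list includes an SAE, other safety concerns, retinal detachment and macular hole. For a study-eye adverse event judged severe, "serious consideration should be given to discontinuing the subject from the study". Leaving is final: "If a subject discontinues from the study, he or she will not be allowed to re-enter the study."

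Four provisions govern what happens afterwards:

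- **5.1:** "All adverse events occurring from Day 0 through Month 12 or Early Withdrawal will be documented and assessed by the principal investigator." A subject who discontinues early is also contacted 7 days after the last injection or study visit.
- **4.5.2:** an early termination visit 30 (±7) days after the last injection or study visit covers all adverse events, serious or not, with the final-visit assessments.
- **5.5.4:** "Subjects who have an ongoing study drug-related SAE at study completion or at discontinuation from the study will be followed", until the event resolves or is judged permanent or stable. Other reported events are followed only until they resolve or participation ends.
- **4.8.2 to 4.8.4:** safety data from all 20 subjects are summarized and endpoint rates are given as a percentage of patients enrolled, yet "Analyses of efficacy and safety will be based on available cases, without imputation for missing values".

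**The concern.** In a safety study, subjects who have been harmed are the ones whose later course matters most. Here harm is a listed ground for leaving the study, not only for stopping the injections, and nothing keeps a subject who leaves in the scheduled visits or the Month 18 and 24 interviews. Missingness in the primary outcome can therefore depend on that outcome.

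Three things would not be collected after the early termination visit: new, repeat or delayed events; the further course of SAEs judged unrelated to study drug; and Month 12 acuity. If those who leave are at higher risk of later events, the rates reported for later periods describe mainly the subjects who tolerated treatment. Neither the available-case rule nor the enrolled denominator corrects for this.

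**Working it through.** The plan has no figure to reproduce. The 20 subjects are chosen on feasibility (4.8.1), no SAE or dropout rate is given, and 3.4 says event occurrence is hard to estimate. The check is therefore a reading of the text followed by illustrations on stated assumptions.

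**1. What is still collected once a subject leaves**

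| Item | Collected? | Source |
|---|---|---|
| Triggering event | Yes, whatever its cause | 5.1, 4.8.2 |
| Events up to about 30 days after the last injection or visit | Yes | 5.1, 4.5.2 |
| Ongoing drug-related SAE | Yes | 5.5.4 |
| Ongoing SAE judged unrelated | No further follow-up provided for | 5.5.4 |
| New, repeat or delayed events to Month 24 | Not provided for | 5.1, 3.1 |
| Month 12 acuity | Not provided for | 4.5.2, 3.3 |

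**2. Could the situation arise?** For an assumed SAE risk p per subject, P(at least one in 20) = 1 − (1 − p)^20. This is 64% at p = 5% and 88% at p = 10%. An SAE does not force withdrawal, so these are probabilities that the question comes up, not that someone leaves.

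**3. Person-time.** Planned follow-up is 20 × 24 = 480 person-months. One month is credited for the early termination visit, taking the last visit as the time of exit.

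- Exit time uniform over 24 months: mean loss per subject = 23² / (2 × 24) = 529 / 48 = 11.02 months. Two exits lose 22.0 (4.6%) and four lose 44.1 (9.2%).
- All exits at Month 6: loss per subject = 24 − 6 − 1 = 17 months. Two exits lose 34 (7.1%) and four lose 68 (14.2%).

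**4. Effect on a later-event rate.** Suppose 4 of 20 leave and the risk of a later event is 5% in the other 16.

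| Later risk in the 4 who left | True rate in all 20 | Available cases | % of enrolled |
|---|---|---|---|
| 20% | (16 × 0.05 + 4 × 0.20) / 20 = 8.0% | 0.8 / 16 = 5.0% | 0.8 / 20 = 4.0% |
| 5% (equal) | 20 × 0.05 / 20 = 5.0% | 5.0% | 4.0% |

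Available cases understate the rate only if those who leave have the higher later risk. The enrolled denominator understates it even when risks are equal, because unobserved subjects count as event-free.

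**5. Precision.** If no later event is seen among n subjects followed, the one-sided 95% upper bound is 1 − 0.05^(1/n): 13.9% for n = 20, 15.3% for n = 18 and 17.1% for n = 16.

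**The case against.** A reader might infer that subjects with an SAE must leave and that their harm disappears from the safety results. The documents do not support that. The reasons in 4.6 are permissive, and even a severe study-eye event calls only for consideration. The triggering event is documented and counted whatever its cause, so the subject already contributes to the incidence of SAEs. The 7-day contact and the 30-day visit capture all adverse events in that window.

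Nor do the documents show that harm will be understated in every case. As the equal-risk row shows, available-case rates can be unbiased. The exit numbers are assumed, and twelve of the 24 months rest on two telephone interviews, so a lost person-month in year 2 carries less information than one in year 1. The plan does not specify a person-time analysis, and this is a small, uncontrolled, descriptive study.

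Section 4.6 also has an incomplete phrase about adverse events just before the no-re-entry sentence. An instruction may be missing there, but its content cannot be known.

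These points narrow the concern but do not remove it. Discretion exercised because of harm still makes the loss depend on outcome. The two early contacts cover about one month of what may be 18 remaining months. Section 5.5.4 provides for no new events. Staying in the study without injections is already normal: observation is permitted from Month 3 (4.4), and every subject is off study drug in year 2 (3.1).

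**Conclusion.** The point holds in limited form. The plan allows a subject to be withdrawn from the study for a safety reason and then provides only about one further month of general adverse event capture, while its primary objective runs to Month 24. The first event is not lost; what can be lost is what happens later.

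The likely size is modest: 4.6% to 9.2% of planned person-months for 2 to 4 exits at uniform times, and 7.1% to 14.2% if all occur at Month 6. These ranges rest on assumed exit numbers and times, and they measure lost observation, not bias. Understatement of later event rates needs a higher later risk in those who leave if available cases are used; with the enrolled denominator it needs only some later risk among them. The change is worth making because it is cheap and protects the primary outcome. The gap does not invalidate the study.

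**What to change.** Leave the listed reasons in 4.6, and all clinical decisions, with the investigator as they are. Then:

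1. State in 4.6 and 5.1 that a treated subject who stops study drug, or is withdrawn for a safety reason, and who still consents, keeps the Month 12 assessment where feasible and the already planned Month 18 and 24 adverse event interviews. Say that these contacts are not barred by the no-re-entry rule.
2. Include events found this way in the primary adverse event tables. Report the reason for and time of each discontinuation, and the number of subjects under observation in each period.
3. Reconcile the denominators in 4.8.3 and 4.8.4, so that subjects no longer observed are not silently counted as event-free.
4. Reconcile 5.1, which documents adverse events to Month 12, with the Month 18 and 24 review in 3.1 and Appendix A. Complete the broken phrase in 4.6.

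The cost is a short amendment and, for a few subjects, at most one visit and two calls that were already in their schedule.

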## 4.7 STUDY DISCONTINUATION

This study may be terminated by Southeast Retina Center at any time. Reasons for terminating the study may include the following:

- The incidence or severity of adverse events in this or other studies indicates a potential health hazard to subjects
- Subject enrollment is unsatisfactory
- Data recording is inaccurate or incomplete

## 4.8 STATISTICAL METHODS

### 4.8.1 Analysis of the Conduct of the Study

There is no formal sample size calculation in this pilot study. As this is a phase I study, a sample size of 20 patients is chosen, making sure that it is feasible financially to conduct the study and logically to complete the study within 2-3 years. If and when the study is planned for a phase II randomized control trial, appropriate statistical analysis will be determined.

### 4.8.2 Safety Analyses

*All non serious and serious* adverse events, angiographic assessments, physical examinations, vital signs, ocular examinations and visual acuity measurements from all 20 subjects will be utilized to summarize safety data for this pilot study.

### 4.8.3 Efficacy Analyses

1. **Primary Endpoint-** See Section 3.3.1

2. **Secondary Endpoints-** See Section 3.3.2

All subjects will be used in analysis of primary and secondary outcome parameters. Rates for the endpoints at the suggested time points will be presented as a % of the patients enrolled. Analysis of Variance will be used to assess for role of variables in for the endpoints. Variables will include # Ranibizumab injections, other therapies, baseline acuity, age, gender, etc.

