eyes demonstrated decrease lesion size but branching choroidal vessels were unchanged. A press release from QLT Inc. (QLT Inc. 2009) reported results from the EVEREST prospective, randomized study evaluating ranibizumab monotherapy versus PDT monotherapy versus ranibizumab/PDT combination therapy for 61 eyes with Asian PCV. At 6 months the ranibizumab monotherapy, PDT monotherapy, and ranibizumab/PDT combination groups gained 9.2, 7.5, and 10.9 letters, respectively. Complete polyp regression occurred in 29%, 71% and 78% of eyes in the ranibizumab monotherapy, PDT monotherapy, and ranibizumab/PDT combination groups, respectively (QLT Inc. 2009).

The above data evaluating anti-VEGF therapy for PCV is limited by a relatively small number of treated eyes, short follow-up and absence of comparison groups. However, given the encouraging results of the above limited data along with the known favorable results of anti-VEGF therapy for neovascular AMD, as well as the overlap between exudative AMD and PCV, further evaluation of anti-VEGF therapy for PCV is needed. In addition, evaluation of anti-VEGF therapy for PCV has primarily occurred in an Asian population and little or no data exist for African-American and Caucasian populations. In fact, African-Americans are hardly represented in neovascular AMD anti-VEGF trials. Ethnic differences in PCV may well affect treatment responses due to genetic makeup, variances in the natural history of disease, and living environments.

We previously enrolled 20 non-Asian PCV eyes and evaluated intravitreal ranibizumab (0.3mg and 0.5 mg) for exudative PCV. Subjects included 16 African-Americans (12 female, 4 male) and 3 male Caucasians. The mean age was 63.6 years and the mean follow-up for the present ongoing study is 18 months. Mean baseline BCVA was 20/127 (range, 20/16-20/500) and CPT was 298  $\mu$ m. Mean BCVA increased from baseline by 1.2 and 1.5 ETDRS lines at 12 and 24 months, respectively. Four of 14 eyes and 3 of 12 eyes gained  $\geq 3$  lines BCVA at 12 and 24 months, respectively. Mean CPT decreased from baseline by 53  $\mu$ m and 67  $\mu$ m at 12 and 24 months, respectively. Eyes received a mean of 7.2 injections during a mean follow-up of 19 months. Visually

significant ocular adverse events included cataract progression (n=3), mild vitreous hemorrhage (n=2), and macular hole (n=1). No systemic drug-related adverse events were observed.

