### **Secondary Outcome Measures**

- Month 3, 6, 9, 12 best corrected visual acuity at 4 meters – rates for gain of 5,10 and 15 or more letters
- Month 3, 6, 9, 12 best corrected visual acuity at 4 meters- rates for loss of 15 or more letters
- Median and Average best corrected visual acuity at 4 meters- gain/loss (letters) at 3,6,9,12 months.
- Mean change from baseline in central foveal thickness over time up to 12 months as assessed on OCT
- Mean change from baseline in macular volume overtime up to 12 months.
- Proportion of patients with no evidence of fluid from CNV as assessed by OCT at 12 months.
- Mean change from baseline in the total area of CNV fluorescein angiographic leakage overtime up to 12 months.
- Mean change from baseline in total area of ICG CNV lesion size (including polyps and deep choroidal vessels) overtime up to 12 months.
- Fluorescein and ICG angiograms and fundus photographs will also be graded at each time point compared to baseline as unchanged, resolved, improved, worsened, or cannot determine. For the FA and ICG evaluations, “resolved” will be defined as no leakage and no evidence of polyps or PCV choroidal lesion; “improved” will be defined as decreased leakage and/or decreased size, number, or hyperfluorescence of polyps and/or PCV choroidal lesion; and “worsened” will be defined as increased leakage and/or increased size, number or hyperfluorescence of polyps and/or PCV choroidal lesion. For fundus photography evaluations, “resolved” will be defined as no evidence of PED, subretinal fluid, hemorrhage, or hard exudate; improved will be defined as a decrease in PED,

subretinal fluid, hemorrhage, or hard exudate; and “worsened” will be defined increase in PED, subretinal fluid, hemorrhage, fibrosis, or hard exudates.

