### **3.4 SAFETY PLAN**

The safety assessments to be conducted for this study are listed in Section 4.5 and Appendix A.

Serious adverse events of intravitreal injection such as endophthalmitis, retinal detachment and significant vitreous hemorrhage will be reported and monitored. Potential serious adverse events related to study drug such as significant uveitis, hypertension, thromboembolic event, or poor wound healing will be reported and monitored. Serious ocular adverse events such as major subretinal hemorrhage, vitreous hemorrhage and 6-line loss rate will be reported and monitored. Serious adverse events such as hospitalizations, surgeries, emergency room admissions and death will be reported and monitored.

Given the small population studied in this Phase I trial, it will be difficult to estimate the adverse event occurrences. Unmasking procedures or treatment recommendations related to drug or the study in particular are not necessary. Any death in the study population will lead to review and assessment while withholding drug injections for enrolled patients until fully reviewed. If two or more patients suffer thromboembolic events, drug injections will also be withheld for all enrolled patients until review and assessment occur.

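### Sections 4.8.3 and 4.8.4 give conflicting denominators for visit-based rates; followed as written, 4.8.3 reports 15-letter loss at its lowest possible value when acuity is missing

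*Combined protocol and SAP*

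**What the plan says.** Section 4.8.3 (Efficacy Analyses) uses all subjects for the primary and secondary outcomes and sets the denominator: "Rates for the endpoints at the suggested time points will be presented as a % of the patients enrolled". Enrolment is 20 subjects (4.1.1, 4.8.1).

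Section 4.8.4 (Missing Data) says: "Analyses of efficacy and safety will be based on available cases, without imputation for missing values".

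The visit-based rates are listed under Secondary Outcome Measures in Section 3.3. They comprise gains of 5, 10 and 15 or more letters at Months 3, 6, 9 and 12; one harm measure, "Month 3, 6, 9, 12 best corrected visual acuity at 4 meters- rates for loss of 15 or more letters"; and one anatomical proportion, "Proportion of patients with no evidence of fluid from CNV as assessed by OCT at 12 months".

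Section 4.8.2 also brings acuity into the safety summary: "visual acuity measurements from all 20 subjects will be utilized to summarize safety data for this pilot study".

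No section says how a subject without an acuity measurement at a visit is classified when a rate is calculated.

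**The concern.** An available-case rate divides by those measured; 4.8.3 divides by those enrolled. The two agree only if nobody is missing or no event is observed. Otherwise the plan leaves open which figure goes in the table.

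The choice has a direction. Under the enrolled denominator, an unmeasured subject is arithmetically a non-event. For gains and the fluid-free proportion this is conservative. For loss of 15 or more letters it is the reverse, because the harm rate takes its most favourable value. The primary objective is safety and 4.8.2 counts acuity as safety information, so a loss rate should not default to that value without the plan saying so.

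**Working it through.** The plan gives no loss rate, dropout rate or sample-size calculation, so there is no figure of its own to reproduce. The check is direct arithmetic.

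**Inputs.** N = 20 enrolled (4.1.1). One study eye per subject is taken as implied by the twenty eyes to be treated in 3.1. The number of observed losses x and the number unmeasured m are assumptions.

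**Formulas for one visit.**
- Rate under 4.8.3 as written: x/20.
- Measured-eye (available-case) rate: x/(20−m).
- Ratio of the first to the second, for x ≥ 1: (20−m)/20, which is 0.90, 0.80 and 0.70 for m = 2, 4 and 6.
- Highest rate compatible with the data, if every unmeasured subject had the loss: (x+m)/20.

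**Results.**

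| x | m | % of enrolled | % of measured | Gap (points) | Missing counted as losses |
|---|---|---|---|---|---|
| 0 | 2 | 0 | 0 | 0 | 2/20 = 10.0 |
| 0 | 4 | 0 | 0 | 0 | 4/20 = 20.0 |
| 0 | 6 | 0 | 0 | 0 | 6/20 = 30.0 |
| 1 | 2 | 5.0 | 1/18 = 5.6 | 0.6 | 3/20 = 15.0 |
| 1 | 4 | 5.0 | 1/16 = 6.3 | 1.3 | 5/20 = 25.0 |
| 1 | 6 | 5.0 | 1/14 = 7.1 | 2.1 | 7/20 = 35.0 |
| 3 | 2 | 15.0 | 3/18 = 16.7 | 1.7 | 5/20 = 25.0 |
| 3 | 4 | 15.0 | 3/16 = 18.8 | 3.8 | 7/20 = 35.0 |
| 3 | 6 | 15.0 | 3/14 = 21.4 | 6.4 | 9/20 = 45.0 |

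With m = 0 the three rates coincide. With m ≥ 1 and x ≥ 1, x/20 is always below x/(20−m). The complete-data rate among the 20 must lie between x/20 and (x+m)/20, so the enrolled figure is the lower end of that range.

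**Scale.** The gaps of 0.6 to 6.4 points are small against sampling error. The exact (Clopper-Pearson) 95% interval is 3.2% to 37.9% for 3/20 and 4.0% to 45.6% for 3/16.

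**The case against.** **The plan may not mean this.** Section 4.8.4 covers efficacy and safety and rules out imputation, and counting an unmeasured subject as a non-event amounts to imputation. A reader might infer that the plan definitely codes missing acuity as no loss, but the text does not establish that. One can read 4.8.4 as governing denominators, in which case it contradicts 4.8.3. One can also read 4.8.3 as governing rates and 4.8.4 as governing means and the analysis of variance, but no sentence draws that line. What stands is that the two sections need reconciling, and that 4.8.3 taken literally has the stated effect.

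**Harm is captured elsewhere.** This largely stands. Section 5.1 requires worsening of a chronic condition to be recorded as an adverse event. The primary outcome lists severe loss only by way of example ("Examples include 30 letter loss, major subretinal hemorrhage") and extends to other adverse events. Section 3.4 adds: "Serious ocular adverse events such as major subretinal hemorrhage, vitreous hemorrhage and 6-line loss rate will be reported and monitored". Mean and median letter change are reported too. A loss of 15 to 29 letters falls short of the 30-letter example but can still be recorded as an adverse event. The early-termination evaluation should also yield an acuity value if its final-visit schedule means Month 12 (4.5.2, Appendix A), although no rule assigns that value to a scheduled month.

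**Missingness need not depend on outcome.** Section 4.6 names worsening condition as a ground for withdrawal, and a reader might infer that the eyes doing badly will be the ones missing. The documents do not show this. Sections 3.1 and 4.4 allow other therapies on study from Month 3 while monthly visits continue, so worsening eyes can stay and be measured.

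**The earlier study is not evidence here.** Section 1.3 says "We previously enrolled 20 non-Asian PCV eyes and evaluated intravitreal ranibizumab" and gives gain rates on 14 and 12 eyes. A reader might take the shortfall from 20 as a likely dropout rate, or object that the new rates would be on a different basis. Neither inference holds. That study was ongoing, so eyes may not yet have reached the visit. Its figures are per eye, with 16 + 3 = 19 subjects listed for 20 eyes. They concern gains, not losses, and no comparison with it is planned.

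**Conclusion.** The point holds as a minor inconsistency worth correcting. The two sections conflict on the denominator. If 4.8.3 is applied as written, the 15-letter loss rate is (20−m)/20 of the measured-eye rate whenever at least one loss is observed and m subjects are unmeasured. For 1 to 3 losses and 2 to 6 unmeasured, all assumed, the difference is 0.6 to 6.4 percentage points. It is zero if nobody is missing or no loss is observed.

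A reader might go further and say that the plan understates the true loss rate. That would follow only if an unmeasured subject had in fact lost 15 letters, which cannot be known in advance. The endpoint is secondary and descriptive in an uncontrolled pilot of 20, and no test, error rate or decision threshold is affected. The conclusion concerns what the table will mean; it does not call the study's findings into question.

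**What to change.** In 4.8.3, define the Month 3, 6, 9 and 12 rate of loss of 15 or more letters as study eyes with the loss divided by study eyes with acuity measured at that visit, which agrees with 4.8.4. Show n measured and n enrolled beside each visit-based rate. The gain rates and the fluid-free proportion may keep the enrolled denominator, labelled as the conservative figure; with both counts shown, a reader can derive the other version. Adverse-event incidence need not change.

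Optionally, add one bound for the loss rate at each visit with missing eyes counted as losses, (x+m)/20. This is a form of imputation, so 4.8.4 would have to name it as a sensitivity exception to its rule. Its main use is where no loss is observed but some eyes are unmeasured, since both ordinary rates then read 0%.

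The cost is a sentence or two of plan text and a few counts: acuity measurements at four visits, OCT at Month 12, and four further figures if the bound is added. The loss rate becomes slightly less favourable if visits are missed and a loss is observed. If no visit is missed, no rate changes.
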